3. DESCRIPTION OF DESIGN AND TRIAL POPULATION

3.1 OVERALL TRIAL DESIGN AND PLAN

This study will be randomized, parallel-design, dose-ranging, placebo-controlled, double-blind, multi-centre and multi-national. A total of up to approx. 120 male and female patients with active lupus nephritis will be randomized in this trial in about 22 countries. There will be three parallel BI 655064 dose groups (approx. 20, 20 and 40 patients) and one placebo dose group (approx. 40 patients). The patients will be randomized 1:1:2:2 to these dose groups. Randomisation will be done with stratification by ethnicity (Asians vs Non-Asian) and proteinuria at screening $<3\text{g/day}$ or $\geq 3\text{g/day}$ (respectively UP/UC <3 or UP/UC ≥ 3). All patients will receive standard of care (SOC) treatment for lupus nephritis, consisting of a 6 month initial phase with 2-3 g MMF/day starting with high dose steroids which will be tapered down to 10 mg prednisone equivalent within 12 weeks after randomization (Refer to [section 4.2.1](#)), followed by a second phase (from week 26 on) with 1-2 g MMF/day in combination with steroids ≤ 10 mg prednisone equivalent/day. BI 655064 will be administered subcutaneously at 3 different doses. For the first 3 weeks the patients will receive two parallel injections/week on the same day of BI 655064 and/or placebo. Then the patients will receive one injection/week of BI 655064 or placebo for up to 52 weeks (12 months). Patients in the placebo dose group will receive only injections of placebo to BI 655064.

The primary endpoint (complete renal response as defined in [section 5.2](#)) will be assessed at 52 weeks. Patients with at least a partial response at week 52 will be offered to enter a maintenance trial (1293.13).

[figure not shown]

Figure 3.1: 1: Outline of trial design

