has been selected as control group as a placebo treatment add-on to SOC is recommended by Health Authorities (HA) as comparisons for dose finding in phase II trials. In addition there is no approved active comparator. MMF-based SOC was selected based on feedback from international experts who in the majority presently recommend MMF. For reasonable comparison and analysis, harmonization of steroid treatment is needed and a tapering schedule is provided which is followed by all patients. ACR and EULAR/ERA-EDTA guidelines recommend to taper steroids down to lowest effective dose. The 10 mg prednisone equivalent target was selected based on external expert recommendation. This amount is looked upon as balance between side effects induced by long-term steroid-treatment and efficacy. The 12 week time point to reach the 10 mg is selected as immunosuppressive therapy is expected to have reached full effect at that time. BI 655064 is expected to be at steady state for some weeks at that time too.. Ideally, patients entering the trial would not have started an induction therapy before randomization; however, it is anticipated that some patients who might have already started a short term induction therapy with SOC might benefit from the combination treatment with BI 655064. According to feedback from external experts, it's not expected that short term induction treatment before randomization will have a major impact on the outcome of a 1 year endpoint. An analysis on the effect of prior treatment with abatacept showed that patients who are naïve to induction treatment had the best response, whereas those who had received >3 months induction showed the poorest response ([R15-3717](#)).

In this trial (1293.10) start of induction treatment prior to randomization is limited to 6 weeks as this will allow for some prior treatment with MMF while maintaining a level of homogeneity to better assess treatment effect in this Phase 2 study. High dose steroids have significant impact on the short term response and have potentially relevant side effects. To keep the population included in the trial more homogenous and to avoid increased risk of side-effects, the total amount of i.v. steroids has to be limited. A total amount of 1.5 g of i.v. steroids is recommended by ACR ([R12-4273](#)) and EULAR/ERA-EDTA ([R12-4921](#)) for induction therapy (3x500 mg i.v.). For severe cases a maximal total amount of 3 g of iv steroids may be considered (3x1000 mg i.v.).

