4.2 CONCOMITANT THERAPY, RESTRICTIONS, AND RESCUE TREATMENT

4.2.1 Rescue medication, emergency procedures, and additional treatment(s)

There are no special emergency procedures to be followed.

Background medication:

All patients will receive standard of care (SOC) treatment for lupus nephritis based on MMF:

SOC Initial phase (week 1 – 26):

- MMF: patients who are already on MMF of 2 g/day or a maximum of 3 g/day should stay at same MMF dose, provided that they have tolerated it well. Patients who start treatment with MMF or patients with a dose <2g/day should be increased to a stable MMF dose of 2g/day. It is recommended not to increase MMF above 2g/day to reduce the risk of severe side-effects of MMF. In case of side effects related to MMF, a MMF dose < 2g/day is allowed.
- AND glucocorticosteroids (GC) (methylprednisolone, recommended 500mg pulse IV for 3 days) followed by oral glucocorticosteroids, tapering to 10mg prednisone equivalent/day within 12 weeks. Tapering of steroids should follow the tapering schedule in [Appendix 10.1](#). Patients who have had already a course of IV steroids (up to a total dose of maximum 3g if it had been considered necessary by the investigator) within 6 weeks prior to randomization should not necessarily repeat it depending on what they received. They should only have necessary pulses to reach a total of 1.5g IV steroids. E.g : if they have already received 2 pulses of 500mg, they will just receive one additional pulse. If they have already had 3 *500 mg, they simply do not repeat any IV pulse. If considered necessary by the investigator, a maximal dose of 1000 mg methylprednisolone per day for up to 3 days (maximal 3000mg) is acceptable.

SOC week 26 – 52:

- Mycophenolate mofetil (MMF) 1 to 2 g/day stable + low-dose (≤ 10 mg/day) prednisone-equivalent

From week 26 only, in case of side effects: MMF may be reduced to 1g/day or in case of non tolerability, patients could be switched to Azathioprine (AZA) 2mg/kg/day + (≤ 10 mg/day) prednisone-equivalent low-dose daily.

In patients who experience a worsening or a flare, the investigator is allowed to increase the steroid dose for the patient. These patients are allowed to continue treatment with BI 655064 until week 52..

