7.7 DETERMINATION OF SAMPLE SIZE

The aims of this study are two-fold. A first aim is to show a significant non-flat dose-response curve across the different doses and placebo. Additionally to that at least one modelled dose within the dose range considered [0mg, 240mg] should show a benefit of at least 10% compared to placebo.

Assumptions for the efficacy of the different doses are provided in the table below.

Based on these assumptions and the planned sample size of 120 (=40:20:20:40) the success probability is approximately 82% for the base case of approximately 20% treatment benefit compared to placebo (45% vs 25% complete renal response rate at week 52). In case that there is only a minor treatment benefit the false success probability is basically limited by the α -level for the significance testing of the non-flat dose-response curve that is 20%.

Table 7.7:1: Success probabilities under different efficacy assumptions

Dose/ Scenario	0	120	180	240	Max. Effect	Sample Size	Alpha	Delta	Simulated power
Expected A	0.25	0.30	0.38	0.44	0.45	40:20:20:40	20%	10%	82%
Expected B	0.25	0.30	0.38	0.44	0.45	35:35:35:35	20%	10%	81%
Type I	0.25	0.255	0.26	0.265	0.27	40:20:20:40	20%	10%	21%
Shift	0.45	0.5	0.58	0.64	0.65	40:20:20:40	20%	10%	80%
Bad	0.25	0.275	0.30	0.34	0.35	40:20:20:40	20%	10%	49%
Type I Shift	0.45	0.455	0.46	0.465	0.47	40:20:20:40	20%	10%	22%

Success probabilities under different efficacy assumptions for the defined success criteria of 1) Significant non-flat dose-response AND 2) Treatment benefit of at least delta compared to placebo for at least one modelled dose within the considered dose range

Scenarios considered:

- Expected A: Main scenario reflecting assumptions for efficacy of 25% (placebo), 30% (low dose), 38% (medium dose), 44% (high dose) and 45% (maximum efficacy). Sample size considered is 40:20:20:40=120 patients with a 2:1:1:2 allocation.
- Expected B: Same scenario as A but for equal allocation and a larger sample size of 140 total. Shows that 'Expected A' (unequal allocation) with 120 patients provides approximately the same success probability with 120 patients as 'Expected B' (equal allocation) with 140 patients.
- Type I: Scenario reflecting almost no treatment benefit. Difference between maximum efficacy and placebo is 2% only (27%-25%). Shows that error probability is approx. 20% in such a case which is driven by the alpha for dose-response curve testing.

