Rationale for change		The reason of deletion of the sentence is that it was misleading. This restriction is not included in the primary endpoint definition. It is also not included in the statistical part (section 7). During the trial, patients could need steroids for other reason than Lupus Nephritis (including emergency situation), therefore some flexibility must be possible for the investigator to treat adequately the patient. This is also done in other trials in this field. Details on how to handle steroid dosing and responder's patients will be clarified in TSAP.
Section to be changed		5.2 & 5.3
Description of change		Clarification of the baseline in screening biopsy
Rationale for change		Clarification
Section to be changed		5.3.5.1
Description of change		Whenever a patient comes to a visit and reports of an (S)AE related to infections which occurred in the interval since the last visit, then he/she is routinely asked whether they have been seen/treated by a physician and whether blood samples had been taken in that context. Should this be answered in the affirmative then efforts should be undertaken to collect the respective information
Rationale for change		On DMC request, meeting 15 May 2018.
Section to be changed		5.3.6
Description of change		Sentence added: "The reliable contraception should be used in female patient before starting MMF therapy and the study drug, during the treatment and until 50 days after stopping MMF and the study drug (and until 90 days after stopping AZA in case of AZA is used). A list of contraception methods meeting these criteria is provided in the patient information. Sexually active men must be ready to use condoms ^s during treatment with MMF/AZA and for at least 90 days after cessation of MMF/AZA treatment"
Rationale for change		Clarification on contraception recommendations, with the use of MMF/ AZA.
Section to be changed		5.3.6
Description of change		Addition of the sentence: "Similarly, potential drug exposure during pregnancy must be reported if a partner of a male trial participant becomes pregnant. This requires a written consent of the

		pregnant partner”
Rationale for change		Information about pregnant partner displayed.
Section to be changed		6.2.3.3
Description of change		Clarification of follow up visits to be performed when discontinuation
Rationale for change		Clarification

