D1	Prohibited medication use	
 • Azathioprine during weeks 0-26 • Cyclophosphamide 6 months prior to randomization through Week 52 • Cyclosporine-Tacrolimus during 4 weeks prior to randomization through Week 52 • Any biologic B-cell depleting therapy (e.g. anti-CD20, anti-CD22) or Abatacept during 12 months prior to randomization through Week 52 • anti-Blyss 3 months prior to randomization for non renal SLE or 12 months for renal SLE through Week 52 • Investigational medication for 6 months or 5 half lives prior to randomization through week 52 • IV glucocorticoids during Week 40-52. (Manual iPDs)	PPS/ (TBD at MQRM/ BRPM)
D2	Non-permitted oral steroid use	Patient used more than 10 mg per day of oral steroid at any time during the interval from week 40 to week 52.	PPS/ (TBD at MQRM/ BRPM)
D3	Non-permitted MMF dose	MMF >3g per day up to week 26 or average MMF >2.5 g per day after week 26	PPS/ (TBD at MQRM/ BRPM)
G	Trial specific		
G1	Failure to remove patient from therapy	As described in CTP section 3.3.4.	PPS/ (TBD at MQRM/ BRPM)
Z	Other		
Z1	Other iPDs affecting efficacy and possibly safety		PPS/ (TBD at MQRM/ BRPM)
Z2	Other iPDs affecting safety only		None

*The numbering of exclusion criteria changed with one or more of the protocol amendments. The numbering, reflected in the data sets and in later eCRFs, is shown in brackets.

Proprietary confidential information © 2020 Boehringer Ingelheim International GmbH or one or more of its affiliated companies

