Definition/derivation of CRR for patients who prematurely stop trial medication

The rules below will be applied to derive CRR/PRR/MRR for the ITT:

Proprietary confidential information © 2020 Boehringer Ingelheim International GmbH or one or more of its affiliated companies

- (1) If the reason for discontinuation of treatment is ‘Lack of efficacy’ or AE type is ‘Worsening of disease under study’, then CRR will be defined as ‘Non-responder’.
- (2) If the patient used prohibited meds known to impact CRR following discontinuation of study med, then CRR will be defined as ‘Non-responder’.
- (3) If neither #1 or #2 apply and treatment duration ≥ 46 weeks, then use the lab data collected at Visit 16-EOT/Week 52 to derive the endpoints. If there is no lab data at Visit 16-EOT /Week 52, then use the lab data closest to 52 weeks that is within 6 weeks prior to week 52.
- (4) If neither #1 or #2 apply and treatment duration < 46 weeks, then CRR will be defined as ‘Non-responder’.

Note that patients handled with the above rules are included in the ITT population. They would only be included in the PPS if they complete 46 weeks of the treatment regimen.

For patients who took study drug for < 46 weeks, continued to participate in the trial and have urine collections and serum creatinine determinations, their data will be displayed in a listing.

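### A patient whose flare is treated with extra oral steroid while on study drug can count as a week-52 complete responder, but one who stops drug for worsening disease cannot

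*Protocol*

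**What the plan says.** **Background steroid.** Protocol 3.1 describes the second SOC phase, from week 26, as MMF "in combination with steroids ≤ 10 mg prednisone equivalent/day". Appendix 10.1 sets the same ceiling from week 13. Protocol 3.2 gives the reason: "harmonization of steroid treatment is needed and a tapering schedule is provided which is followed by all patients".

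**Flare.** Protocol 4.2.1 repeats the ceiling for weeks 26-52 and then adds: "In patients who experience a worsening or a flare, the investigator is allowed to increase the steroid dose for the patient". No cap is stated. It continues: "These patients are allowed to continue treatment with BI 655064 until week 52". Protocol 3.3.4.1 gives the other route: the investigator may let a patient with a flare discontinue and start rescue therapy.

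**Scoring.** SAP 5.1 builds CRR from week-52 urine protein and eGFR, with no steroid condition. SAP 6.6.1 lists four rules that lead either to non-response or to use of late laboratory data. All four stand under "Definition/derivation of CRR for patients who prematurely stop trial medication".

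**Deviation D2.** SAP Table 6.2: 1 defines it as: "Patient used more than 10 mg per day of oral steroid at any time during the interval from week 40 to week 52". Its consequence is exclusion from the per-protocol set (PPS), still to be decided at a later review meeting.

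**History.** The rationale for the Amendment 6 change to protocol 5.2 says: "Details on how to handle steroid dosing and responder's patients will be clarified in TSAP". The visible SAP contains no steroid rule for responders other than D2.

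**The concern.** Two patients can have the same worsening of lupus nephritis and be scored differently in the primary analysis, depending on whether the investigator raises the steroid and keeps study drug going, or stops it. The first is judged on week-52 laboratory values that the extra steroid may have improved. The second is a failure. A management decision that may follow how well the assigned treatment works therefore enters the endpoint.

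If BI 655064 is effective, flares and steroid increases should be more frequent on placebo. Some placebo patients would then reach CRR through added steroid, and the week-52 difference would understate the drug effect. That difference feeds both the dose-response test and the 10-point benefit used to choose the target dose (protocol 7.3.1).

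The PPS does not correct this. If D2 is applied, a rescued patient leaves the denominator and is not counted as a failure.

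**Working it through.** **1. Tracing a patient after a flare through the visible rules**

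| Course after an LN flare | ITT, week 52 | PPS |
|---|---|---|
| Stops drug; reason is lack of efficacy or worsening of the study disease | Non-responder (6.6.1, rule 1) | Kept only if 46 weeks were completed and no other deviation excludes |
| Stops drug, then uses prohibited medication known to affect CRR | Non-responder (rule 2) | As above |
| Stays on drug; oral steroid above 10 mg/day at some time in weeks 40-52 | Scored on week-52 laboratory values | May be excluded under D2; decision open |
| Stays on drug; oral steroid above 10 mg/day in weeks 13-39 only | Scored on week-52 laboratory values | Kept; scored on laboratory values |

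Protocol 7.3.1 and 7.5 do not change the last two rows, because they fail only patients withdrawn for non-response and non-completers. Extending rule 2 to on-drug use would not catch them either. The visible Table 4.2.2.1: 1 lists IV but not oral glucocorticoids, and 4.2.1 expressly allows the increase.

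**2. Reproducing the plan's figure**

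Protocol 7.7 states: "success probability is approximately 82% for the base case of approximately 20% treatment benefit compared to placebo". Inputs from 7.3.1 and 7.7: rates 25/30/38/44%, n = 40:20:20:40, one-sided α = 20%, benefit of at least 10 points.

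- Normal approximation, 240 mg against placebo: power = Φ[(Δ − 0.8416·SE₀)/SE₁]. With Δ = 0.19, pooled SE₀ = √(2 × 0.345 × 0.655/40) = 0.1063 and SE₁ = √((0.25 × 0.75 + 0.44 × 0.56)/40) = 0.1042, this gives 83.3%.
- MCPMod simulation (40,000 runs; three assumed sets of shape parameters, because the figure is not shown): 81.5-83.5%. The Shift and Bad rows also reproduce: 79.5-81.3% against 80%, and 48.7-49.9% against 49%. The two Type I rows come out 1.6-2.5 points high.

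**3. Illustration under assumed conversion**

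Let r be the share of would-be non-responders who flare, stay on drug, have steroid raised and score CRR because of it. The observed rate becomes p + r(1 − p). The documents give no value for r, so every row after the first is an assumption. On placebo, 30 of 40 patients are expected non-responders, so r = 10% means 3 patients.

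| r placebo | r active | Placebo | 240 mg | Difference (points) | Simulated success |
|---|---|---|---|---|---|
| 0 | 0 | 25.0% | 44.0% | 19.0 | 81.5-83.5% |
| 10% | 10% | 32.5% | 49.6% | 17.1 | 75-77% |
| 10% | 5% | 32.5% | 46.8% | 14.3 | 67-68% |
| 10% | 0 | 32.5% | 44.0% | 11.5 | 57-59% |
| 20% | 10% | 40.0% | 49.6% | 9.6 | 50-52% |
| 5% | 10% | 28.75% | 49.6% | 20.85 | not run |

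With equal r the difference is (1 − r) × 19, so it shrinks even without imbalance. If rescue were more frequent on active drug it could grow (last row). The Shift row of Table 7.7 does not cover this, because it adds about 20 points to every arm and keeps the 19-point gap.

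**The case against.** **The control may be as intended.** The objective (protocol 2.2) defines SOC by reference to 4.2.1, and 4.2.1 contains the flare permission for every arm. A reader might infer that the trial has lost its placebo-plus-SOC control, but the documents do not support that. Scoring week-52 values whatever the steroid use is a coherent treatment-policy choice. What stands is that neither document states this choice, and rules 1 and 2 depart from it.

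**Amendment 6 was deliberate.** The sponsor gave reasons: steroids may be needed for other conditions, including emergencies, and other trials in the field allow this. That argues against replacing the primary derivation and against counting all steroid use. It does not explain why the handling promised for the SAP is missing.

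**The sizing rate.** A reader might infer that 25% presupposed failure scoring for these patients, so that 82% no longer holds. The Amendment 6 rationale says the restriction was never in the statistical section. Protocol 2.1 gives 20-30% CRR on SOC with no steroid condition, and 7.7 calls the rates guesstimates. The inference fails.

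**Stopping is a different event.** Stopping for worsening means leaving drug for guideline rescue, and any stop before 46 weeks is non-response anyway. This is partly right: the two routes are not identical. Both begin with the same flare, however, and the choice is discretionary.

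**Unseen text.** SAP 7.4.2 has no visible content, and the history table mentions a corticosteroid exposure table that the visible 7.2 lacks. A steroid sensitivity analysis may exist. It would not settle the PPS handling or the conflict between D2 and 4.2.1.

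**Conclusion.** On the visible text, a patient treated for a flare with oral steroid above 10 mg/day while on study drug can be a complete responder in the primary ITT analysis. Patients who stop for worsening, or who use prohibited medication after stopping, cannot. D2 is the only visible steroid consequence. It affects only the PPS, by possible exclusion, and it conflicts with the permission in 4.2.1. The ceiling and the permission in 4.2.1, Appendix 10.1 and D2 must be reconciled. This review takes no position on which clinical rule is right.

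The likely direction is dilution, on the assumption that rescue is at least as frequent on placebo as on active drug. The size is not known. The table above shows sensitivity to an assumed r and is not evidence that this trial loses power. Nor would a rule limited to weeks 40-52 bring the analysis back to 82%, because it misses earlier rescue. The point is worth acting on because the gap is clear and cheap to close, not because a loss has been shown.

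**What to change.** - **Add a derivation (SAP 6.6.1 and 7.4).** Before final database lock, pre-specify a second ITT derivation of CRR, PRR and MRR at week 52, analysed by the same methods and shown beside the current one. A patient with a recorded LN worsening or flare, and oral steroid above 10 mg/day for that flare at any time in weeks 40-52 (the D2 window), is a non-responder whether or not study drug was stopped. Steroid given for another reason does not count.
- **PPS.** Keep these patients as non-responders; do not exclude them under D2.
- **Tabulate by arm.** Count the affected patients, and separately those with flare-related increases in weeks 13-39, which the D2 window misses.
- **State the choice.** Say which derivation is primary and why, and reconcile D2 with protocol 4.2.1 and Appendix 10.1.

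**Cost.** SAP wording and one derived flag. D2 already requires the steroid dose in weeks 40-52, protocol 5.3.6 already records worsening of the underlying disease as an adverse event, and the SAP already carries alternate CRR derivations. The new work is a blinded review of the reason for each increase, plus the tabulation for weeks 13-39. Response rates in the added derivation will be slightly lower. What steroid a patient may receive does not change.
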